## **6 Sequence of planned analysis**

### **6.1 Main efficacy analysis**

No interim analysis of efficacy data is planned. However, two database locks are planned. The first database lock will be performed when all patients have conducted the Day 15 visit (Visit 4) of the first flare in the study and the main efficacy analysis will be conducted. The main efficacy analysis includes primarily all efficacy endpoints for the first flare.

All collected data for the first flare, i.e. at a minimum data up to and including the Day 15 visit and at a maximum data up to 12 weeks, will be analyzed. Allocation to analysis populations and all efficacy analyses including data up to Day 15 will be considered as final.

Prior to the first database lock all tasks and criteria defined in the data management plan must be completed and documented. After the database lock the blind will be broken and results will be generated. The SAP will be finalized and signed prior to the first database lock and subsequently the breaking of the blinding. The database lock will be approved by relevant study personnel.

After the data transfer for the main efficacy analysis has occurred, the database will be unlocked to continue with data entry activities for Visit E, Visit 5 and follow-up by phone that had not taken place at the cut-off date for the first database lock and for subsequent flares. However, no changes to the data up to Day 15 should be performed except that ongoing AEs at Day 15 for the first flare might need to be updated.

## **6.2 Final analysis**

The final analysis will include efficacy analyses from subsequent flares and safety and exploratory analyses from all flares. It will be performed when all patients have completed the study. The database will be locked a second time following the same procedure as described in Section 6.1.

If updates to the SAP are needed after the first database lock, all changes will be described and the updated SAP will be finalized, locked and signed prior to final database lock. Any changes to the planned analyses will also be described in the CSR.

## **6.3 Reporting**

The CSR for the study will be written after the final database lock and include data and results from both the first and subsequent flares. The results generated for the main efficacy analysis, i.e. all tables, figures and listings that only includes data up to and including the Day 15 visit, will remain unchanged.

Any post-hoc analyses included in the CSR, which were not identified in the SAP, will be clearly identified as such in the relevant Section of the CSR.

## **7 Sample size determination**

Up to totally 169 patients can be randomized in the study. Initially 159 patients will be randomized, 53 to triamcinolone and 106 to anakinra (53 to 100 mg and 53 to 200 mg). As described in section 4.2, up to a maximum of 10 extra patients can be randomized.

The sample size calculation is based on the change in pain intensity on a VAS 0 to 100 mm from baseline to the average over 24 to 72 hours. A sample size of 106 patients randomized to anakinra and 53 patients randomized to triamcinolone is required to ensure a power of 80 % to reject the null hypothesis of no difference between anakinra and triamcinolone assuming a true difference of 12 mm on VAS mean change and a SD of 25 mm when using a 2-sided test with a significance level of 5 %.

## 8 Analysis populations

Sections 8.1, 8.2 and 8.3 presents the analysis sets used in the statistical analyses.

### 8.1 Intention-to-treat (ITT)

The ITT population is the primary analysis population for the primary and secondary efficacy endpoints, comprising all randomized patients grouped according to randomized treatment and stratum. Presentations of efficacy endpoints for subsequent flares will also be based on the ITT population.

### 8.2 Per-protocol population (PP)

The PP population will comprise all ITT patients who have no major protocol violations potentially affecting the primary efficacy endpoint. The patients will be grouped according to actual treatment received during the first gouty arthritis flare. Patients assigned to an incorrect strata will be grouped according to actual baseline BMI and ULT information. Patient assignment to the PP population will be performed prior to breaking the blind. The PP population will only be used for analyses of efficacy endpoints for the first flare.

The following criteria are classed as major protocol deviations/violations and will exclude patients from the PP population:

- Incorrectly included:
  - Not fulfilling the ACR/EULAR 2015 Gout Classification Criteria.
  - Not fulfilling baseline pain intensity in the index joint of  $\geq 50$  on a 0 to 100 VAS or missing baseline pain intensity assessment.
  - The onset of the current ongoing flare is more than 4 days prior to first IMP injection (days from onset to first IMP injection will be calculated in full days allowing patients with time from onset to randomization  $< 5$  days to be included in the PP population).
- Missing VAS pain intensity assessments at all of the following timepoints: 24, 48 and 72 hours.
- More than one incorrect intake of rescue medication, i.e. type or outside permitted time window at any of the following timepoints: 24, 48 or 72 hours (see Section 18.1).
- Missing more than one daily IMP injection occasion during the first 3 days of treatment.
- Administration during the first three days of IMP that have had a significant temperature excursion.

## **9 General considerations for statistical analysis**

All statistical tests will be 2-sided and performed using a 5 % significance level, if not stated otherwise. Results will be presented as the point estimate for each treatment group, the estimated difference between groups, the associated 95 %, 2-sided confidence interval and p-value. P-values from statistical analyses will be presented to 3 decimal places with values below 0.001 displayed as <.001 and confidence intervals will be presented to one more decimal place than the raw data.

Continuous data will be summarized using descriptive statistics: n, mean, SD, median, minimum and maximum, unless otherwise stated. Minimum and maximum will be presented to the same number of decimal places as the raw data and mean, SD, standard error of the mean and median will be presented to one more decimal place than the raw data.

Categorical data will be summarized using counts and percentages. Percentages will be suppressed when the count is zero, however the category will still be displayed. The denominator for all percentages will be the number of patients within the treatment group for the population of interest, unless otherwise indicated. Percentages will be presented to one decimal place.

Statistical analyses will be performed using SAS software, Version 9.1 or later (SAS Institute Inc, Cary, North Carolina, United States).

### **9.1 Handling of missing data and outliers**

Patients should continue in the study even if study treatment is withdrawn and every effort should be made to complete the assessments according to the protocol. The evaluation of patient-assessed pain using VAS and Likert scales have repeated assessment time points and repeated measures models will be used to handle missing data, i.e. no imputation is needed. To evaluate the robustness of this model for the primary endpoint, sensitivity analyses including multiple imputation methods will be performed (see Section 14.1.2). For the secondary time-to-event analyses, patients who do not have an event at the time for analysis will be censored at the last

time point with recorded information. For other secondary endpoints the analyses will be based on observed data.

In case of missing or incomplete dates or times, no imputations will be made in the listings of data. Rules on how to handle partially or completely missing dates or times in calculations are described in Section 18.

## **9.2 Multicenter studies**

No effects of centers will be evaluated in this study.

## **9.3 Multiple comparisons and multiplicity**

No adjustment for multiplicity will be performed.

## **10 Patient disposition**

All patient disposition data will be presented by triamcinolone, the combined anakinra group, anakinra 100 mg/day, anakinra 200 mg/day and overall.

The number and percentage of patients who were randomized, initiated treatment, completed and discontinued study together with the reasons for discontinuations will be presented both for each treated flare and for the full study. If a patient prematurely discontinues the study during a flare, all prior flares are completed (i.e. only the last flare may be prematurely discontinued). If the discontinuation is after the Day 15 visit, the flare is considered completed (i.e. all flares may be completed even if the patient has prematurely discontinued the study). Otherwise, the patient has prematurely discontinued the flare with the reason for discontinuation the same as the reason for premature discontinuation of the study.

The number of weeks in the study and the number of treated flares experienced by the patients during the study will be presented by descriptive statistics for the ITT and safety population. Further, the number and percentage of patients experiencing 1 treated flare, 2 treated flares, 3 treated flares, etc. will also be presented for the ITT and safety population.

The total number and percentage of patients who completed treatment and discontinued treatment together with reason for discontinuation will be tabulated for each flare and overall for the safety population.

The number and percentage of patients in each strata will be presented for the ITT, PP and safety populations. Stratification data will be received from the IWRS system and actual strata will be derived using CRF data.

The distribution of patients at each site will be tabulated for the ITT population, sorted by descending number of patients.

A table displaying the number and percentage of patients with each type of major protocol deviations that lead to exclusion from the PP population will be presented. Percentages will be based on the ITT population.

The number and percentage of patients in the ITT population, the PP population and the safety population will be presented.

## **11 Demographics and baseline characteristics**

### **11.1 Demographics**

The demographic data, including age, sex, race, and ethnicity will be presented by descriptive statistics for the ITT, PP and safety populations (see Section 18.1).

### **11.2 Baseline characteristics**

Baseline characteristics of gouty arthritis, such as age at diagnosis, disease duration, and number of gouty arthritis flares during the past 12 months will be presented for the ITT, PP, and safety populations (see Sections 18.1 18.4, and 18.5).

The number of patients who completed patient/caregiver IMP injection training and patient diary training will be presented for the ITT population.

The reasons NSAIDs and colchicine are inappropriate will be presented for the ITT, PP and safety populations.

Body height, body weight, BMI, waist circumference, body temperature, systolic and diastolic blood pressure, and pulse (see Section 18.3) will be presented using descriptive statistics for the ITT, PP, and safety populations. For subsequent flares, body weight, BMI, body temperature, systolic and diastolic blood pressure, and pulse will be presented.

Each of the ACR EULAR Gout Classification Criteria at baseline will be presented for the ITT, PP, and safety populations.

Medical examination of current flare (Time of pain onset prior to IMP injection, the number and distribution of joints involved and the index joint) will be presented for each flare for the ITT, PP, and safety populations.

### **11.3 Medical and surgical history and concurrent illnesses**

All medical and surgical history data will be coded using the MedDRA Version 19.1 and the same version will be used throughout the study.

Medical and surgical history at baseline will be presented by SOC and PT for the ITT, PP, and safety populations. Medical and surgical history reported after randomization will be presented separately (see Section 18.6).

Detailed information on the presence of the following selected comorbidities will be presented in a separate table for the ITT, PP, and safety populations: eGFR category, current or previous symptoms of heart failure, diabetes mellitus, hypertension, obesity, cardiovascular disease, hyperlipidemia, cerebrovascular disease and osteoporosis (see Sections **Error! Reference source not found.**, 18.8, 18.9, 18.10 and 18.11).

Data from physical examination will be presented as “normal” or “abnormal” at Day 1 and Day 15 for each flare for the ITT, PP, and safety populations. Any persisting abnormalities should be stated each time the examination is performed in medical history and new abnormalities should be recorded as AEs.

Baseline ECG will be presented for each flare.

## **12 Prior and concomitant medication**

All prior and concomitant medication will be coded using the latest version of World Health Organization drug dictionary (WHODD B2 DEC\_2016 DDE [Enhanced]) and the same version will be used throughout the study.

The preferred term grouped by ATC level 4 will be used for presentation and sorted in descending order of frequency in total (all treatment groups together) at the top in the table.

Prior medication, concomitant medication at randomization and onset of new concomitant medication after randomization during the study will be presented separately for the ITT, PP and the safety populations (see Section 18.12).

ULT use, initiated after randomization in addition to the study drug will be presented per flare for patients in stratum ULT use=no for the ITT, PP and the safety populations (see Section 18.14).

## **13 Study drug compliance**

Study drug compliance, calculated as percentage, i.e. actual number of syringes administered divided by number of syringes dispensed times 100 will be presented for each flare and overall by descriptive statistics (see Section 18.15).

## 14 Efficacy analyses

### 14.1 Primary efficacy endpoint

The primary efficacy endpoint will be analyzed using the ITT population (primary population for evaluation) and will be based on observed data i.e. no missing data imputation for the primary analysis.

The primary endpoint is the change in patient-assessed pain intensity from baseline to 24 to 72 hours (average of the assessments performed at 24, 48 and 72 hours) for the patients' first flare (see Section 18.16 for time windows for pain intensity assessments).

Patients will score their pain intensity in the joint most affected at baseline (i.e., the index joint) on a 0 to 100 VAS, ranging from no pain (0) to unbearable pain (100) (see Section 18.17).

The comparison of primary interest is between anakinra (100 mg and 200 mg combined) and triamcinolone, and the null and alternative hypotheses with regard to this are defined as:

$$H_0: \mu_{\text{anakinra}} = \mu_{\text{triamcinolone}}$$

$$H_A: \mu_{\text{anakinra}} \neq \mu_{\text{triamcinolone}}$$

The primary endpoint will be estimated using a MMRM analysis with the measurements on the individual time points as responses (baseline, 6, 12, 18, 24, 48 and 72 hours), and with treatment (anakinra 100 mg, anakinra 200 mg and triamcinolone), ULT use (yes/no), BMI (<30.0 and  $\geq 30.0$  kg/m^2), visit and treatment-visit-interaction as fixed effects and center as random effect. The model is expressed as:

$$y_{ij} = \text{time}_j + \text{treat}_k + \text{time} \times \text{treat}_{jk} + \text{ULT}_l + \text{BMI}_m + \text{center}_n + \varepsilon_{ij}$$

where

$y_{ij}$  is the response for patient  $i$  on visit  $j$

$\text{time}_j$  is the visit effect (baseline, 6, 12, 18, 24, 48 and 72 hours),  $j=1, \dots, 7$

$\text{treat}_k$  is the treatment effect,  $k=1, 2, 3$

$\text{ULT}_l$  is the ULT strata effect (yes, no),  $l=1, 2$

$\text{BMI}_m$  is the BMI strata effect (<30.0,  $\geq 30.0$ ),  $m=1, 2$

$\text{center}_n \sim N(0, \sigma_c^2)$  and  $\varepsilon_{ij} \sim N(0, \sigma^2)$

The analysis will be based on a restricted maximum likelihood (REML) approach. The following order of covariance matrices will be used until convergence is met:

- i. Unstructured
- ii. Heterogeneous Toeplitz
- iii. Heterogeneous first order autoregressive
- iv. Homogeneous Toeplitz
- v. Homogeneous first order autoregressive

- vi. Heterogeneous compound symmetry
- vii. Homogeneous compound symmetry

Kenward-Roger approximation will be used to estimate denominator degrees of freedom and adjust standard errors.

The estimated mean change from baseline to 24 to 72 hours for each treatment group (anakinra and triamcinolone), the estimated difference between the groups and the associated 95 % confidence interval and p-value based on this model will be presented.

The assumptions of normality and homogeneity of variance will be assessed by inspection of normal probability plots and residual plots.

The estimated mean change from baseline to 24 to 72 hours and the associated 95 % confidence interval for anakinra (combined and each dose group) and triamcinolone will also be presented graphically.

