- The comparison of primary interest is between anakinra (100 mg and 200 mg combined) and triamcinolone. The primary endpoint will be estimated using a mixed model repeated measures analysis with the measurements on the individual time points as responses (baseline, 6, 12, 18, 24, 48 and 72 hours), and with treatment (anakinra 100 mg, anakinra 200 mg and triamcinolone), ULT use (yes/no), BMI (<30.0 and ≥30.0 kg/m²), visit and treatment-visit-interaction as fixed effects and center as random effect. An unstructured covariance matrix will be used to account for within-subject correlation. The estimated mean change from baseline to 24-72 hours for each treatment group (anakinra and triamcinolone), the estimated difference between the groups and the associated 95 % confidence interval and p-value based on this model will be presented. Further, each of the two doses of anakinra, 100 mg and 200 mg, will be compared to triamcinolone using the same model as for the primary comparison.
- The secondary time-to-event endpoints will be analyzed using a stratified log-rank test, with ULT use (yes/no) and BMI (<30.0 or ≥30.0 kg/m²) as stratification factors.
- The secondary continuous endpoints will be analyzed using an analysis of covariance including factors for treatment, ULT use (yes/no) and BMI (<30.0 or ≥30.0 kg/m²) and baseline value as covariate.

The secondary binary endpoints will be analyzed using a logistic regression model with treatment, ULT use (yes/no) and BMI (<30.0 or ≥ 30.0 kg/m²) as explanatory variables. Safety tabulations of adverse event data and laboratory data will be performed.

Continuous variables will be summarized using the number of patients, the mean, the standard deviation, the median, the minimum value, and the maximum value. Categorical variables will be summarized using frequency counts and percentages.

2 Abbreviations and definition of terms

ACR	American College of Rheumatology
ADA	Anti-drug antibodies
AE	Adverse event
Anakinra	Recombinant interleukin 1 receptor antagonist
ANC	Absolute neutrophil count
BMI	Body mass index
CAPS	Cryopyrin-associated periodic syndrome
CDASH	Clinical data acquisition standards harmonization
CDISC	Clinical data interchange standards consortium

CKD	Chronic kidney disease
CLIA	Clinical laboratory improvement amendments
CRO	Contract research organization
CRP	C-reactive protein
ECG	Electrocardiogram
eCRF	Electronic case report form
EEA	European economic area
ED	Emergency department

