9.3.3 Analysis related to primary objective

9.3.3.1 Primary endpoint

The primary endpoint is the change in patient-assessed pain intensity from baseline to 24-72 hours (average of the assessments performed at 24, 48 and 72 hours) for the patients' first flare.

The comparison of primary interest is between anakinra (100 mg and 200 mg combined) and triamcinolone, and the null and alternative hypotheses with regard to this are defined as:

$H_0: \mu_{\text{anakinra}} = \mu_{\text{triamcinolone}}$

$H_A: \mu_{\text{anakinra}} \neq \mu_{\text{triamcinolone}}$

The primary endpoint will be estimated using a mixed model repeated measures analysis with the measurements on the individual time points as responses (baseline, 6, 12, 18, 24, 48 and 72 hours), and with treatment (anakinra 100 mg, anakinra 200 mg and triamcinolone), ULT use (yes/no), BMI (<30.0 and ≥ 30.0 kg/m²), visit and treatment-visit-interaction as fixed effects and center as random effect. An unstructured covariance matrix will be used to account for within-subject correlation. The estimated mean change from baseline to 24-72 hours for each treatment group (anakinra and triamcinolone), the estimated difference between the groups and the associated 95 % confidence interval and p-value based on this model will be presented.

The assumptions of normality and homogeneity of variance will be assessed by inspection of normal probability plots and residual plots.

The primary efficacy analysis mixed model repeated measures approach assumes that the underlying missing data mechanism is missing at random (MAR). Since the MAR assumption may not hold, a tipping point analysis will be used for performing sensitivity analysis under the missing not at random (MNAR) assumption. For data that is missing, a shift parameter (with a range of values) will be added to imputed values. This will assess the value of the shift parameters, for anakinra and triamcinolone, which would overturn the conclusions of the primary analysis. The tipping point analysis will assume that the missing outcomes on anakinra and triamcinolone will vary independently including scenarios where the dropouts on anakinra have worse outcomes than triamcinolone.

The full details of the sensitivity analyses to assess the robustness of the primary analysis will be pre-specified in the SAP.

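### The primary MMRM gives each arm its own baseline mean, so the primary contrast is an unadjusted change score that loses precision and passes on chance baseline imbalance

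*SAP*

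**What the plan says.** SAP 14.1 defines the primary analysis as an MMRM "with the measurements on the individual time points as responses (baseline, 6, 12, 18, 24, 48 and 72 hours". The time term in the model equation "is the visit effect (baseline, 6, 12, 18, 24, 48 and 72 hours", indexed 1 to 7, and the model has "visit and treatment-visit-interaction as fixed effects and center as random effect", plus ULT and BMI strata. Protocol 9.3.3.1 and the synopsis give the same specification. The reported quantity is "The estimated mean change from baseline to 24 to 72 hours for each treatment group (anakinra and triamcinolone", with the difference between groups. Neither document states that the arms share a baseline mean, and neither enters baseline VAS as a covariate for this endpoint.

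The same or a similar model serves the subgroups (SAP 14.1.1), the per-protocol analysis (14.1.2.1), the tipping-point analysis (14.1.2.2 and 14.1.2.3), the VAS and Likert profiles (14.2.1, 14.2.2) and the dose comparisons (14.3.1.1). The imputation step of the tipping-point analysis uses baseline VAS, but the model then fitted is the primary one.

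Other continuous endpoints are handled differently. The synopsis plans an analysis of covariance with treatment and strata "and baseline value as covariate". The SAP does this for tenderness and swelling (14.3.1.8), CRP and SAA (14.3.1.9) and SF-36 physical functioning (17.1).

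**The concern.** Treatment and treatment-by-visit terms that include the baseline visit let the three arms differ before any treatment is given. The model then estimates three baseline means that randomisation makes equal, and it subtracts each arm's own baseline in full. That amounts to assuming a slope of 1 for later pain on baseline pain.

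A slope below 1 is more plausible here. Patients enter at VAS 50 mm or more, so some regression to the mean is expected. The plan's own onset and response endpoints also express improvement as a percentage of baseline: if pain falls in proportion to its starting value, a 50% fall corresponds to a slope of 0.5.

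With a slope below 1, the primary confidence interval is wider than it needs to be, and a chance baseline difference moves the treatment estimate. Randomisation is stratified by ULT use and BMI but not by pain, so the design does not prevent such a difference. No planned sensitivity analysis adjusts for baseline, so none would reveal the effect.

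**Working it through.** **1. The plan's own figure.** For 80% power at the two-sided 5% level, SAP 7 plans 106 patients on anakinra and 53 on triamcinolone, "assuming a true difference of 12 mm on VAS mean change and a SD of 25 mm". The standard error of the difference is 25 × √(1/106 + 1/53) = 25 × 0.1682 = 4.21 mm. The noncentral t distribution gives 80.9% power, so the stated figure is reproduced. The 25 mm is the SD of the change score, which matches an unadjusted change analysis.

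**2. What the model estimates.** Any contrast of later minus baseline values removes terms that are constant over time, so ULT, BMI and center drop out. The arm-by-visit means are saturated. With complete data and one within-patient covariance matrix, the contrast therefore equals the raw difference in mean change, whichever covariance structure on the SAP's list is fitted.

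This was checked by generalised least squares on simulated data with 159 patients, seven times, ULT, BMI and random center. The baseline SD was 14.4 mm, the later SDs 20–26 mm and the slope about 0.59.

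| Quantity | Estimate (mm) | SE (mm) |
|---|---|---|
| Raw change-score difference | −1.4415 | – |
| Model as written | −1.4415 (same under compound symmetry) | 3.80 |
| Common baseline mean | −0.68 | 3.68 |
| As written, 7% of post-baseline values missing | −1.79 | 3.82 |
| Common baseline mean, same missing values | −1.01 | 3.70 |

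The common baseline mean lowers the variance by about 6% in this setting. In a second setting, baseline SD was 13 mm, later SDs were 20–25 mm and the correlation was 0.7 per step. The SEs were 3.82 and 3.53, about 14% less variance.

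**3. Precision.** Let s0 be the baseline SD and b the slope of the 24–72 h mean on baseline. Then

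variance of change = adjusted variance + (1 − b)² × s0², so adjusted variance = 625 − (1 − b)² × s0².

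Neither s0 nor b is in the documents. The assumed values of s0 are 10 mm and 14.4 mm; the latter is the SD of a uniform distribution on 50–100, 50/√12. Power is for 106 against 53 and a 12 mm difference, by the noncentral t distribution.

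| s0 (mm) | b | (1 − b)² × s0² | Variance reduction | Power |
|---|---|---|---|---|
| 10 | 0.25 | 56.3 | 9.0% | 84.4% |
| 10 | 0.5 | 25.0 | 4.0% | 82.5% |
| 10 | 0.7 | 9.0 | 1.4% | 81.5% |
| 14.4 | 0.25 | 116.6 | 18.7% | 88.2% |
| 14.4 | 0.5 | 51.8 | 8.3% | 84.2% |
| 14.4 | 0.7 | 18.7 | 3.0% | 82.1% |
| either | 1 | 0 | 0 | 80.9% |

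At b = 0 and s0 = 14.4 mm the reduction would be 33%. For b = 0.25–0.5, the unadjusted analysis would need 159 × (625/adjusted variance − 1) = 7 to 36 more patients to match the adjusted one. Counted as patients saved from 159, the figure is 6 to 30.

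**4. Imbalance.** If the arms differ at baseline by D, the expected contrast shifts by (1 − b) × D in size. At s0 = 14.4 mm, one standard error of D is 14.4 × 0.1682 = 2.42 mm, giving a shift of 1.2 mm (b = 0.5) to 1.8 mm (b = 0.25). The 95% range of D is ±4.7 mm; it carries 3.3, 2.4 or 1.4 mm into the estimate at b = 0.3, 0.5 or 0.7, which is 12–28% of 12 mm. For s0 = 10 mm and b = 0.5, the 95% figure is 1.65 mm. For one dose against triamcinolone (53 against 53, s0 = 14.4 mm), one standard error of D is 14.4 × √(2/53) = 2.8 mm.

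**The case against.** The strongest reply is that nothing here is invalid. The endpoint is defined as a change from baseline and the contrast estimates that change. It is unbiased over randomisations, and the type I error is controlled. The sample size rests on the SD of the change, so the trial has its stated power, and the plan only forgoes a possible gain. All of this stands. The imbalance effect is conditional on the baseline difference that happens to occur; it is not a bias of the procedure.

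The size is also open to challenge, because s0 and b are assumptions. The top of the range needs the larger SD and the lowest slope together, and at b = 0.7 the gain is about one power point, or 2–5 patients. The second simulated setting makes baseline nearly uninformative: its correlations with the 24, 48 and 72 h values are 0.24, 0.17 and 0.12, which favours adjustment. That also stands and limits the claim on magnitude, but not the claim about the model.

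Two further points carry less weight. Keeping baseline among the responses retains patients whose baseline is missing, a case SAP 8.2 foresees; a common baseline mean retains them as well. The plan is also consistent by model type, since every repeated pain measure treats baseline in this way and the baseline-adjusted endpoints are single-time analyses. That describes the pattern but gives no reason to leave the primary endpoint unadjusted.

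**Conclusion.** The point holds. As specified in both documents, the primary contrast is an unadjusted difference in change scores: exactly so with complete data, approximately so with missing values. The stratification terms add no adjustment to it. This follows from the model and does not depend on assumptions about the data.

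The cost is lost efficiency and exposure to chance imbalance. It is neither bias nor underpowering. For a baseline SD of 10–14.4 mm, an SD of change held at 25 mm and slopes of 0.25–0.5, it is about 1.5 to 7 power points; it shrinks towards nil as the slope approaches 1. The change should be made because it costs almost nothing and uses a value the trial already collects, but the primary test would remain valid without it.

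**What to change.** Keep the seven-time-point MMRM, the contrast and the covariance sequence, but constrain the baseline mean to be the same in all three arms: no treatment term at baseline, and treatment-by-visit effects at post-baseline times only. This version keeps patients with a missing baseline.

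The alternative is to model post-baseline values only, with baseline VAS and baseline-by-visit as covariates. It drops patients without a baseline unless that value is imputed, so the constrained version is preferable for the ITT analysis.

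Use the same specification in SAP 14.1.1, 14.1.2, 14.2.1, 14.2.2 and 14.3.1.1, with the Likert baseline in 14.2.2. The cost is one sentence in SAP 14.1 and in Protocol 9.3.3.1, the matching synopsis text, and a small program change before unblinding. No new data and no further patients are needed.
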